8.3. Variables

Table 1. Immunocompromising Conditions definition

Variable	Role	Data source(s)	Operational definition
Immunocompromising Conditions	Cohort Definition	HealthVerity Vaccine Data	
Subjects will be categorized into the following 12 mutually exclusive IC groups based on the algorithm detailed in Figure 1:
 
Symptomatic HIV/AIDS, solid malignancy, bone marrow transplant recipients, organ transplant recipients, rheumatologic or other inflammatory conditions, primary immunodeficiencies, other intrinsic immune conditions, chronic kidney disease or end stage renal disease, hematologic malignancy, immunosuppressive treatment only, antimetabolites only, or >1 IC condition.

PFIZER CONFIDENTIAL

Table 1. Immunocompromising Conditions definition

Variable	Role	Data source(s)	Operational definition
			
Subjects falling into more than one of these categories will be categorized as having >1 IC condition.
 
At a minimum, subjects will be required to have one inpatient claim or two outpatient claims on separate days with the IC condition of interest in the baseline period. In cases when >14 days of treatment are required it will be based on the dispensed day supply or distinct days of treatment in the baseline period.
 
The main diagnosis codes to identify IC conditions are presented in ANNEX 1. LIST OF STAND ALONE DOCUMENTS.

Table 2. Vaccination Status definitions

Variable	Role	Data source(s)	Operational definition
Any vaccination	Cohort Definition	HealthVerity Vaccine Data	
Patients with a claim for any vaccine will be considered vaccinated with any vaccine based on the following codes:
 
Pfizer/BioNTech: 91300, 0001A, 0002A, 59267100001, 59267100002, 59267100003
 
Moderna: 91301, 0011A, 0012A, 80777027310, 80777027399, 80777027315, 80777027398
 
Johnson & Johnson: 91303, 0031A, 59676058005, 59676058015
 
Source: https://www.cdc.gov/vaccines/programs/iis/COVID-19-related-codes.html

Fully Vaccinated	Cohort Definition	HealthVerity Vaccine Data	
Patients will be considered fully vaccinated if they meet any of the following definitions:
 
Two claims for Pfizer/BioNTech vaccine on separate days with >14 days of follow-up after the 2nd vaccination date. No claims for any other vaccines are allowed.

PFIZER CONFIDENTIAL

Table 2. Vaccination Status definitions

Variable	Role	Data source(s)	Operational definition
			
 Two claims for Moderna vaccine on separate days with >14 days of follow-up after the 2nd vaccination date. No claims for any other vaccines are allowed. One claim for the Johnson & Johnson (J&J) vaccine with >14 days of follow-up after the 1st vaccination date. No claims for any other vaccines are allowed
Partially vaccinated	Cohort Definition	HealthVerity Vaccine Data	
Patients will be considered partially vaccinated if they meet any of the following criteria:
 
 One claim for Pfizer/BioNTech vaccine with > 18 days of follow-up following first vaccination date and no claims for any other vaccine. One claim for Moderna vaccine with > 25 days of follow-up following first vaccination date and no claims for any other vaccine. One claim for J&J vaccine with \leq14 days of follow-up following first vaccination date and no claims for any other vaccine.

Table 3. Patient Characteristics and Vaccine Utilization variable definitions

Variable	Role	Data source(s)	Operational definition
Age	Patient Characteristics	HealthVerity Vaccine Data	The number of years between the index date and the patient birth year. If multiple birth years are reported for the same HealthVerity ID, the maximum birthyear will be used. Age will be reported in the following categories: 16 – 17, 18 – 29, 30 – 39, 40 – 49, 50 – 64, 65 – 74, 75 – 84, and 85+. Adolescents age 12-15 will also be reported as data accumulates over monthly data cuts. Continuous statistics including mean, standard deviation (SD), median (Q1-Q3).

PFIZER CONFIDENTIAL

Table 3. Patient Characteristics and Vaccine Utilization variable definitions

Variable	Role	Data source(s)	Operational definition
			minimum, and maximum, will also be summarized.
Sex	Patient Characteristics	HealthVerity Vaccine Data	Sex will be reported as Male ('M'), Female ('F'), and Unknown
US Geographic Region	Patient Characteristics	HealthVerity Vaccine Data	
US geographic region will be derived from the patient state and categorized into the following:
 
Northeast – Connecticut, Maine, Massachusetts, New Hampshire, Rhode Island, Vermont, New Jersey, New York, Pennsylvania
 
Midwest – Indiana, Illinois, Michigan, Ohio, Wisconsin, Iowa, Kansas, Minnesota, Missouri, Nebraska, North Dakota, South Dakota
 
South – Delaware, District of Columbia, Florida, Georgia, Maryland, North Carolina, South Carolina, Virginia, West Virginia, Alabama, Kentucky, Mississippi, Tennessee, Arkansas, Louisiana, Oklahoma, Texas
 
West – Arizona, Colorado, Idaho, New Mexico, Montana, Utah, Nevada, Wyoming, Alaska, California, Hawaii, Oregon, Washington
 
Other – Puerto Rico

Payer/insurance coverage on index date	Patient characteristics	HealthVerity Vaccine Data	Payer on index date will be reported as the following categories: Commercial, Medicaid, Medicare, Unknown, or missing. If multiple payers are reported on the index date, those will be captured under an ad-hoc "Multiple" category.
Vaccine Administration Setting	Patient characteristics	HealthVerity Vaccine Data	Vaccine administration setting will be determined based on the reported place of service for the claim. Prescription claims will be assumed to have occurred in the Pharmacy setting. The most common settings will be reported.
Conditions that place or may place patients at risk of Severe COVID-19 (6 months prior)	Patient Characteristics	HealthVerity Vaccine Data	Baseline comorbid conditions that place or may place patients at risk of Severe COVID-19 infection will be assessed in the 6 months prior to index vaccination. The ICD-10-CM, ICD-10 Procedure Coding System (ICD-10-

PFIZER CONFIDENTIAL

Table 3. Patient Characteristics and Vaccine Utilization variable definitions

Variable	Role	Data source(s)	Operational definition
			PCS), Current Procedural Terminology (CPT-4), and Healthcare Common Procedure Coding System (HCPCS) codes used to identify these conditions are based on the Sentinel COVID-19 Natural History Master Protocol (https://www.sentinelinitiative.org/methods-data-tools/methods/master-protocol-development-covid-19-natural-history)
Prevention seeking behavior (at baseline)	Patient Characteristics	HealthVerity Vaccine Data	
These variables will be assessed during the 12 month baseline period:
 
Telephone or Telehealth visits defined as a claim with any of the following procedure codes (G2012, G2010, G2061-G2063; 99205-99205, 99212-99215, 99421-99423, 99441-99443, G0425-G0427, G0406-G0408)
 
COVID-19 laboratory tests defined as a claim with any of the following CPT-4 codes (87635, 86318, 86328, 86769, 87426, 86408, 86409, 86413)
 
Flu vaccinations defined as a claim with the following procedure codes (90653-90664, 90666-90668, 90724, 90470, 90672, 90673, 90685-90688)
 
The cumulative proportion of IC and non-IC subjects receiving their first dose of COVID-19 vaccine, by month, starting from December 2020 until most recent data.

Acute Respiratory Infection Hospitalization (at baseline)	Patient Characteristics	HealthVerity Vaccine Data	Any inpatient claim that occurs in the 12 month baseline period with a diagnosis of J00-J06, J09-J18, J20-J22 will be reported
Follow-up time	Patient Characteristics	HealthVerity Vaccine Data	The number of days between the index date and the earliest of the following: end of the study or end of continuous insurance enrollment
IS drugs use	Patient Characteristics	HealthVerity Vaccine Data	The proportion of subjects with IC conditions and usage of IS drugs for >14 days during the baseline period will be reported, as well as use within 14 days and 28 days within receipt of the first vaccine dose. IS drugs exclude low-dose [<60mg/day] prednisone.

PFIZER CONFIDENTIAL

Table 3. Patient Characteristics and Vaccine Utilization variable definitions

Variable	Role	Data source(s)	Operational definition
COVID-19 supportive medication use	Patient Characteristics	HealthVerity Vaccine Data	The use of medications considered supportive for COVID-19 will be assessed in the 12-month baseline period including remdesivir, dexamethasone, doxycycline, norepihephrine, methylprednisolone, lopinavir/ritonavir, eculizumab, sarilumab, tocilizumab, losartan, azithromycin, hydroxychloroquine, siltuximab, colchicine, and convalescent plasma. Codes used to identify these treatments will be based on the Sentinel COVID-19 Natural History Master Protocol
Other baseline medication use	Patient Characteristics	HealthVerity Vaccine Data	Medications for pre-existing conditions per the Sentinel COVID-19 Natural History Master Protocol (eg, angiotensin converting enzyme inhibitors (ACE), angiotensin-receptor blockers (ARB)).
Vaccine utilization	Patient Characteristics	HealthVerity Vaccine Data	Patterns of uptake. The proportion of IC and non-IC patients who are partially and fully vaccinated with BNT162b2 (or any other vaccines), at different calendar months and follow-up periods (eg, 7 days post dose 2, 14 days post dose 2). Mean, median, minimum, and maximum time between receipt of the first and second dose of BNT162b2 (or any other vaccine)

Table 4. Breakthrough Cases Definition

Variable	Role	Data source(s)	Operational definition
Breakthrough SARS-CoV-2 infection	Outcome	HealthVerity Vaccine Data	Among patients who meet the definition of fully vaccinated, a breakthrough SARS-CoV-2 infection will be defined by evidence of a claim with a diagnosis code of U07.1 that occurs >14 days after the second vaccination date. The first claim with a diagnosis of COVID-19 after this time will be used to assess mean and median time from the second dose until the breakthrough case

PFIZER CONFIDENTIAL

Table 5. COVID-19 Healthcare resource use and Costs definitions

Variable	Role	Data source(s)	Operational definition
Emergency department (ED) visit	Outcome	HealthVerity Vaccine Data	An outpatient claim with a place of service = 23 that occurs after the breakthrough COVID-19 diagnosis date or at the same time/episode of care
Outpatient Hospital Visit	Outcome	HealthVerity Vaccine Data	An outpatient claim with a place of service = 22 or 19 or a standard billing code that begins with '13' that occurs after the breakthrough COVID-19 diagnosis date or at the same time/episode of care
Other Outpatient Visit (not ED, not hospital-based)	Outcome	HealthVerity Vaccine Data	An outpatient claim that does not meet the definition for an ED visit or Outpatient hospital visit.
Hospitalization	Outcome	HealthVerity Vaccine Data	A record from the chargemaster data with encounter type of Inpatient OR a series of claims (separated by no more than 2 days) with a place of service = 21 or standard billing codes that begin with '11' or '12' that occur after the breakthrough COVID-19 diagnosis or at the same time/episode of care 1 st admission and readmissions will be differentiated.
Intensive Care Unit (ICU)	Outcome	HealthVerity Vaccine Data	A claim with a procedure code indicative of ICU utilization during a hospitalization that occurs after the breakthrough COVID-19 diagnosis or at the same time/episode of care 1 st admission and readmissions will be differentiated.
Invasive Mechanical Ventilation (IMV) / Extracorporeal Membrane Oxygenation (ECMO)	Outcome	HealthVerity Vaccine Data	A claim with a procedure code indicative of IMV/ECMO utilization during a hospitalization that occurs after the breakthrough COVID-19 diagnosis or at the same time/episode of care Includes both 1 st admission and readmissions.
Inpatient Death	Outcome	HealthVerity Vaccine Data	Death that occurs on or after the date of the breakthrough COVID-19 diagnosis. The date of death will be assumed to be the same as the date of the last recorded encounter in the database.

PFIZER CONFIDENTIAL

Table 5. COVID-19 Healthcare resource use and Costs definitions

Variable	Role	Data source(s)	Operational definition
			
Death information is available from the Charge Description Master (CDM) data and is provided as year-month of death only.
 
Time to death will also be explored.

Length of Stay (LOS)	Outcome	HealthVerity Vaccine Data	
Length of stay (LOS) associated with different types of hospitalization treatments mentioned above (eg, ICU), applicable for first index hospitalization and/or readmissions.

Costs	Outcome	HealthVerity Vaccine Data	
Non-zero costs associated with any of the previously listed Outpatient and Inpatient encounters (but death).
 
Charges may be assessed in sensitivity analyses to interpret the cost data.

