8. RESEARCH METHODS

8.1. Study design

This study will be a retrospective database analysis utilizing data sets within the HealthVerity database (Philadelphia, Pennsylvania) covering the time period 01 December 2018 through 08 July 2021 (or latest data available) to describe the characteristics of subjects with IC conditions vaccinated with BNT162b2 and to evaluate the incidence of SARS-CoV-2 breakthrough infections.

Study period: 01 December 2018 – 08 July 2021 (or latest data available)

Index identification period: 11 December 2020 – 08 July 2021 (or latest data available; inclusive)

Index date: The first record for a SARS-CoV-2 vaccine (primary analysis: BNT162b2; sensitivity analyses: any Mrna, any authorized vaccine) from a medical claim, pharmacy claim, or chargemaster record.

Baseline period: 12-month period prior to the index vaccination date

Follow-up period: Variable period beginning after the index date and continuing until the earliest of the following: end of the study or end of continuous insurance enrollment.

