Eight of the disease groups will include subjects with 1) symptomatic human immunodeficiency virus (HIV)/acquired immunodeficiency syndrome (AIDS); 2) solid malignancy; 3) bone marrow transplant; 4) organ transplant (excluding bone marrow); 5) rheumatologic or other inflammatory condition; 6) a primary immunodeficiency; 7) other immune conditions; and 8) chronic kidney disease (CKD) or end stage renal disease (ESRD). Subjects in these IC groups (shown as “Group 1” in [Figure 1](#)) will be further stratified by treatment status: those with usage of immunosuppressive medications for >14 days anytime during the baseline period and those without any evidence of >14 days of usage of an immunosuppressive medication during the baseline period. Subjects with a bone marrow or

organ transplant will be further stratified by those who received their 1st vaccine dose >100 days prior to their transplant and those who received it <100 days prior to their transplant. Subjects with a solid malignancy will be further stratified by their treatment type: chemotherapy or radiation therapy or immunomodulator, or a mix of these treatments.

The 9th subject group (shown as “Group 2” in [Figure 1](#)) will include those with a hematologic malignancy, required to have usage of an immunosuppressive medication (chemotherapeutic agent, immunomodulator, or systemic corticosteroid) for >14 days anytime during the baseline period; this subject group will be further stratified by their use of an immunosuppressive medication >6 months or ≤ 6 months prior to their index date.

The 10th subject group will include subjects with usage of an immunosuppressive medication (chemotherapeutic agent, immunomodulator, or systemic corticosteroid excluding low-dose [<60mg/day] prednisone) for >14 days anytime during the baseline period, but without any ICD-10-CM diagnosis codes indicating the above listed IC conditions on a healthcare claim anytime during the baseline period. Subjects with >14 days usage of antimetabolites anytime during the baseline period will be excluded from this subject group and placed in the 11th subject group.

[figure not shown]

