ANNEX 3. ICD-10 CODE LIST

IC Condition	ICD-10 Code
HIV/AIDS*	B20-B24
Solid malignancy	
Organ/system malignant tumors	C00-C07; C11-C19; C22-C80; Z85
Neuroendocrine tumors	C7A; C7B; D3A
Neoplasms of uncertain behavior	D00-D49
Bone marrow transplant	Z94.81
Organ transplant	
Complications of transplanted organ	T86
Organ transplant status	Z94 except Z94.81; Z98.85
Rheumatologic or other inflammatory condition	
Sarcoidosis	D86
Amyloidosis Not Otherwise Specified (NOS)	E85
Familial Mediterranean fever	E85.0; M04
Amyloidosis Not Elsewhere Classified (NEC)	E85.1; E85.3; E85.8
Multiple sclerosis	G35
Other Central Nervous System (CNS) demyelination	G36; G37.1; G37.3; G37.8; G37.9
Acute infective polyneuritis	G61.0; G61.9
Acute myocarditis	I40
Polyarteritis nodosa and other	M30
Allergic alveolitis/pneumonitis NOS	T78.40; J67.9
Other alveolar pneumonopathy	J84.01; J84.02; J84.09

PFIZER CONFIDENTIAL

IC Condition	ICD-10 Code
Enteritis and colitis	K50-K52
Lupus erythematosus	L93.0; L93.2; M32
Diffuse connective tissue disease	L94; M35.8; M35.9
Arthropathy with infection	M12.9; M01.X0; M02.10
Crystal arthropathies	M11
Rheumatoid arthritis/inflammatory polyarthropathy	M05-M14
Inflammatory spondylopathies	M46
Polymyalgia rheumatica	M31.5; M35.3
Chronic inflammatory demyelinating polyneuropathy	G61.81
Immune thrombocytopenic purpura	D69.3
Primary Immunodeficiency	
X-linked agammaglobulinemia	D80.8
Common variable immunodeficiency	D83.1; D83.2; D83.8; D83.9
Immunoglobulin A (IgA) deficiency	D80.2
Immunoglobulin G (IgG) sub-class deficiency	D80.3
Severe combined immunodeficiency	D81.1
Di George syndrome	D82.1
Wiskott-Aldrich	D82.0
Ataxia telangiectasia	G11.3
Interferon-gamma/Interleukin 12 axis deficiencies	D84.89
Persistent complement, properdin or Factor B deficiency	D84.1
Received eculizumab for >14 days in the baseline period	
Chronic granulomatous disease	D71
Chediak-Higashi	E70.330
Leukocyte adhesion deficiency	D72: Genetic anomalies of leukocytes
Myeloperoxidase deficiency	D72.89: Other specific disorders of White Blood Cells (WBCs)

PFIZER CONFIDENTIAL

IC Condition	ICD-10 Code
Other immune conditions	
Disorders of immune mechanism	D89
Neutropenia	D70
Functional disorders of neutrophils	D71
Genetic anomalies of leukocytes	D72.0
Decreased leukocyte count	D72.81
Leukocyte disease NEC	D72.89
Leukocyte disease NOS	D72.9
Myelofibrosis	D75.81
Blood diseases NEC	D47.4; D75.89; D75.9; D89.2
Blood diseases NOS	D75.9; D75.89
Immunologic findings NEC	R76; R83.4-R87.4; R89.4

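### The rule for more than 14 days of treatment mixes days of supply with visit counts; read plainly, a clinic drug given singly every 27 days or more cannot meet it on its own

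*Combined protocol and SAP*

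**What the plan says.** Table 1 (Section 8.3) gives the only counting rule in the text: where more than 14 days are needed, "it will be based on the dispensed day supply or distinct days of treatment in the baseline period". It does not assign either measure to a route or claim type, define a day of treatment, or say how many days one administration is worth. The counting window is the baseline, defined in Section 8.1 as the "12-month period prior to the index vaccination date".

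The threshold is used in several places:

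- **Groups 1 to 8 (Section 8.2.1).** Diagnosis alone makes the subject IC. The threshold separates treated subjects from "those without any evidence of >14 days of usage of an immunosuppressive medication during the baseline period".
- **Group 9, hematologic malignancy (Section 8.2.1, repeated in the Annex 3 footnote).** Subjects are "required to have usage of an immunosuppressive medication (chemotherapeutic agent, immunomodulator, or systemic corticosteroid) for >14 days anytime during the baseline period". Here it is a condition of entry.
- **Group 10 (Section 8.2.1).** The same threshold, "but without any ICD-10-CM diagnosis codes indicating the above listed IC conditions on a healthcare claim anytime during the baseline period". Group 11 applies it to antimetabolites. In both, drug use is the only route to IC status.
- **Annex 3, primary immunodeficiency.** One line reads "Received eculizumab for >14 days in the baseline period".
- **Table 3.** The proportion of IC subjects with "usage of IS drugs for >14 days during the baseline period will be reported".

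**The concern.** Day supply measures how long a patient is covered, and distinct treatment days measure how often the patient attends. One cut-off of more than 14 cannot mean the same thing on both scales. A clinic infusion on a medical claim would ordinarily carry no dispensed supply, so it falls naturally under distinct days, one per visit. Section 8.2.1 also admits people without pharmacy benefits, for whom distinct days may be the only measure available. A patient treated throughout the year at long intervals could then fail, while a patient with one short dispensed course passes.

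What is at stake is cohort membership. A hematologic malignancy patient who fails group 9 also fails group 10, which uses the same threshold and, in Section 8.2.1, excludes anyone with a listed IC diagnosis. If no other criterion applies, that patient is counted as non-IC. Membership feeds Aims 1 to 3, the risk difference between non-IC and IC subjects, and the group-specific effectiveness estimates in Section 8.7.

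**Working it through.** The plan states no figure to reproduce here, so the check is a direct count.

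**Inputs from the documents.** Threshold: more than 14 days, so at least 15. Window: 12 months, W = 365 days (366 gives the same results below).

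**Inputs that are assumptions.** (a) The drug has no day supply and each administration date counts as one day. (b) Administration is at a regular interval of d days, one day each time. The documents give no dosing intervals, so d is varied from 7 to 182.

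**Step 1. Most distinct days possible in the window:** floor((W − 1)/d) + 1.

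| Interval d (days) | Maximum count | Reaches 15? |
|---|---|---|
| 7 | 52 + 1 = 53 | yes |
| 14 | 26 + 1 = 27 | yes |
| 21 | 17 + 1 = 18 | yes |
| 26 | 14 + 1 = 15 | only just |
| 27 | 13 + 1 = 14 | no |
| 28 | 13 + 1 = 14 | no |
| 56 | 6 + 1 = 7 | no |
| 182 | 2 + 1 = 3 | no |

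The longest interval that can qualify is 364/14 = 26 days.

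**Step 2. Shortest course giving 15 single administrations:** 14d + 1 days.

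- every 7 days: 99
- every 14 days: 197
- every 21 days: 295
- every 28 days: 393, longer than the window

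So a course every 14 or 21 days also fails if less than about 197 or 295 days of it lies within baseline.

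**Step 3. The other measure.** One fill with a supply of 15 days or more passes alone, so a single 28-day fill qualifies. Fourteen administrations 28 days apart, spanning 13 × 28 + 1 = 365 days, do not.

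**Step 4. Where the failure does not occur.**

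- Multi-day cycles: with 2, 3 or 5 treatment days per 28-day cycle, 15 is reached in 8, 5 or 3 cycles.
- Loading schedules: weeks 0, 2 and 4, then every 4 weeks, give days 0 and 14 plus 13 dates from day 28 to day 364, which is 15. This needs the whole year inside the window. Five weekly doses, then every 4 weeks, give 5 + 12 = 17.
- Injectables dispensed by a pharmacy carry a day supply and can pass on one fill.
- A second qualifying drug admits the patient whatever the first one scores.

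**The case against.** The strongest reply is that the premise is inferred. A reader might take Table 1 to say that infused or injected drugs are counted by visit. It does not: it offers two measures joined by an undefined or. Table 1 defers to Figure 1, and Sections 8.2.1 and 8.7 point to a medication list; neither was in the text available for this review, and either might settle the matter. That stands, and it limits the point to the plain reading of Table 1. If a rule sits elsewhere, Table 1 should point to it.

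A reader might also infer that patients on long-interval agents can never qualify, or that group 9 shrinks to those on oral drugs or steroids. Step 4 rules out the first. Weekly, 2-weekly and 3-weekly infusions of sufficient duration rule out the second.

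Nor are all who fail filed as non-IC. Groups 1 to 8 remain IC by diagnosis, and some hematologic malignancy patients will carry another listed code, such as neutropenia (D70) or decreased leukocyte count (D72.81).

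A reader might further infer that the contrasts are biased toward the null by some stated amount. The documents support neither a size nor a direction, since they do not say that such patients have more breakthrough infections. The effect on the non-IC rate may be small. If an assumed 1% of that cohort were misfiled with r times the rate of the rest, the rate would change by a factor 0.99 + 0.01r: 1.00 at r = 1 and 1.02 at r = 3. Section 8.7 also names no treated-versus-untreated effect measure; the strata in groups 1 to 8 are descriptive.

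Finally, Section 8.7 plans sensitivity analyses on the IC case definition, and Section 8.9 admits that the effect of modifying the published algorithm cannot be assessed. Neither addresses this rule, and the drug requirement for hematologic malignancy is itself one of those modifications (Section 8.2.1), so the published sensitivity and specificity do not cover it.

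**Conclusion.** The point holds in limited form. Table 1 places two different scales under one threshold. Read plainly, an agent given in a clinic and billed without a day supply cannot pass on its own when given singly and regularly every 27 days or more; at 14- or 21-day intervals it passes only if the course is long enough. This rests on counting one day per administration date and on assumed intervals. Failure affects entry to groups 9 to 11, the treatment strata of groups 1 to 8, the eculizumab criterion and the drug-use variable in Table 3. Because the number of subjects concerned is not in the documents, no bias figure should be attached. It is still more than missing detail: applied as written, the rule decides who is IC for some patients on a visit count rather than on exposure, and it should be settled before the cohorts are built.

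**What to change.** In Table 1, for clinic-administered agents without a day supply, replace distinct days with days covered: credit each administration with a coverage period specific to the agent, set by the sponsor and entered in the study drug list, and sum the covered days in baseline. Keep day supply for dispensed drugs. Apply the definition wherever the threshold appears: the strata of groups 1 to 8, entry to groups 9 to 11, the eculizumab line in Annex 3 and the drug-use variable in Table 3. Report how many subjects change group or stratum compared with the distinct-days count, which will supply the size that the documents cannot.

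The cost is one added column in the drug list and a programming change on data already held. The downside is that a few one-off or short-course recipients may be classed as treated. Accepting a small fixed number of administrations, such as two, would be simpler, but it could admit two isolated steroid injections to group 10, so days covered is the better choice.

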8.8. Quality control

Data in HealthVerity's COVID Healthcare database are collected weekly in an electronic format. HealthVerity employs its foundational product to match patients between different data sources with high accuracy. However, not all data points are available in every data source and as a result, not all variables in the database are completely populated. In addition, the database contains both pre- and post-adjudicated claims and, based on the data source, adjudication may or may not be captured. To maximize data completeness and uniformity, it may be necessary to exclude certain data sources from the analysis due to differences in data structure and content.

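### Table 2 sets no minimum gap between the two mRNA claims that define full vaccination, so one dose recorded under two different dates can count as a completed series

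*Combined protocol and SAP*

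**What the plan says.** The BNT162b2 rule in Section 8.3, Table 2 requires "Two claims for Pfizer/BioNTech vaccine on separate days", with more than 14 days of follow-up after the second and no claim for any other vaccine. The Moderna rule matches it: "Two claims for Moderna vaccine on separate days with >14 days of follow-up after the 2nd vaccination date". Neither gives a minimum interval.

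Qualifying codes are pooled by brand: "Pfizer/BioNTech: 91300, 0001A, 0002A, 59267100001, 59267100002, 59267100003". The rule does not ask for two different codes. The Moderna list similarly includes 0011A and 0012A.

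The same table does use product-specific day counts for partial vaccination: "One claim for Pfizer/BioNTech vaccine with > 18 days of follow-up following first vaccination date" and "One claim for Moderna vaccine with > 25 days of follow-up following first vaccination date". These are lengths of follow-up for one-claim subjects, not gaps between claims.

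Section 8.1 takes the index vaccination "from a medical claim, pharmacy claim, or chargemaster record". Section 8.8 says "the database contains both pre- and post-adjudicated claims" and that adjudication may or may not be captured. No section states a rule for duplicate vaccine records. Section 8.7 starts person-time 14 days after the qualifying dose.

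**The concern.** The requirement for different days is the only protection against counting one dose twice, and it works only when both records carry the same date. With three record types and claims at different stages of adjudication, it is plausible that one dose sometimes appears under two nearby dates. There are two consequences.

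- **One-dose subject, two dates.** The subject meets the fully vaccinated definition and, having two claims, no longer fits the one-claim partial definition. Any later infection enters the Aim 2 numerator and the Aim 3 case series.
- **Two-dose subject, first dose under two dates.** There are three claims. Table 2 does not say whether two means exactly two or at least two, or which date is the second vaccination date. One reading starts the clock early; the other drops a subject who did receive two doses.

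The same variable defines the Aim 2 denominator and starts its clock. The plan does set rules for comparable record problems: in Table 5 it joins inpatient claims no more than 2 days apart into one hospitalization, and in Table 3 it resolves conflicting birth years.

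**Working it through.** The plan states no figure here to reproduce; Section 8.5 says there is no formal sample size computation.

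**Timing, from the documents alone.** Let dose 1 be recorded on day 0 and the second claim on day g. Person-time starts on day g + 14, and the first day more than 14 days after the second claim is g + 15. The smallest gap admitted is g = 1, so person-time starts on day 15 and an infection can count from day 16. For g = 1, 2 and 3 the first countable day is 16, 17 and 18. All three fall before a one-claim Pfizer/BioNTech subject passes the >18-day threshold for partial vaccination.

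**Size, by illustration.** The documents give none of these inputs; all are assumptions:
- d = share of first doses also recorded one day later: 1%, 3%, 5%
- s = share of subjects with one dose only: 10%, 20%
- k = one-dose infection rate relative to the two-dose rate: 5
- 100 true at-risk days, and 21 days between real doses

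A duplicate one day after dose 1 moves the start from day 35 (21 + 14) to day 15, which adds 20 days. Per subject, with the two-dose daily rate set to 1:
- two-dose, no duplicate: weight (1−s)(1−d), 100 days, 100 rate units
- two-dose, duplicated, clock starting at the duplicate: weight (1−s)d, 120 days, 20k + 100 = 200 units
- one-dose, duplicated: weight sd, 120 days, 120k = 600 units

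One-dose subjects without a duplicate stay out. Inflation is total units divided by total days.

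Example, s = 10% and d = 3%:
- days = 87.3 + 0.027×120 + 0.003×120 = 90.9
- units = 87.3 + 0.027×200 + 0.003×600 = 94.5
- ratio = 94.5/90.9 = 1.040

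| d | s = 10% | s = 20% |
|---|---|---|
| 1% | 1.3% | 2.0% |
| 3% | 4.0% | 5.9% |
| 5% | 6.6% | 9.8% |

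**Why these are upper figures for these inputs.** Only about 6 of the 20 early days (15 to 21) precede the real second dose; the other 14 follow it. If the fivefold rate applies to those 6 days only, the duplicated two-dose subject contributes 6×5 + 14 + 100 = 144 units instead of 200. The range then falls from 1.3-9.8% to 0.8-7.0%:
- s = 10%, d = 1%: 90.996/90.3 = 1.008
- s = 20%, d = 5%: 87.76/82.0 = 1.070

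**Under the exactly-two reading.** Duplicated two-dose subjects leave the analysis, so a fraction d of the two-dose group is lost. Inflation then comes only from duplicated one-dose subjects:
- s = 10%, d = 1%: 89.7/89.22 = 1.005
- s = 20%, d = 5%: 82.0/77.2 = 1.062

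**The case against.** The strongest reply is that the error is hypothetical and would be seen. The documents list several record types and mixed adjudication, but nowhere say that one dose carries different dates. Table 3 reports the minimum time between doses, so a one-day gap would show. Section 8.8 allows inconsistent sources to be excluded, Section 8.7 promises sensitivity analyses on key design aspects, and Section 8.9 concedes misclassification in general. It stands that the frequency is unknown and that differing dates are an inference. But none of these provisions supplies a rule. A reported minimum of one day would reveal the problem without correcting the rate, and analyses rerun on monthly data cuts need the handling fixed in writing.

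Three stronger readings are tempting and are not supported:
- A reader might infer that any dose recorded twice counts as a full series. Same-date records do not.
- A reader might put the duplicate frequency straight into 1 + d(k−1) and obtain 4%, 12% and 20% at d = 1%, 3% and 5% with k = 5. That formula needs the one-dose share of fully vaccinated person-time. Most duplicates would fall in subjects who did receive two doses, so that share is far smaller: with s = 10% and d = 3%, and equal follow-up, it is 0.003/0.903 = 0.33%, or 1.3% inflation before any early-clock effect.
- A reader might infer that immunocompromised subjects, having more healthcare contact, are affected more and that the comparison with non-immunocompromised subjects is distorted. Nothing in the documents shows this.

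**Conclusion.** The point holds as a defect in a stated rule: as written, Table 2 admits claim pairs one day apart as completed series and leaves the three-claim case undefined. If one-dose infection rates exceed two-dose rates, the error raises the Aim 2 rate; it also admits one-dose infections to the Aim 3 description. Because the exploratory effectiveness estimate depends on who counts as vaccinated, it is probably touched too.

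The documents do not allow the size to be determined. Under the assumptions listed, inflation is at most about 1% to 10%. It is smaller if the one-dose rate applies only to the days before the real second dose, or if three-claim subjects are dropped. It would be larger with more duplicates, more one-dose subjects or a higher relative rate than assumed. The timing result (day 15 for person-time, day 16 for events) rests on the plan's text alone. The change is worth making because it is cheap and removes an avoidable upward bias from a primary objective.

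**What to change.** Add a data step ahead of Table 2:

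1. Collapse same-brand mRNA claims closer together than a pre-set record-linkage window into one dose, dated at the earliest. The 18 and 25 days that the plan already uses as follow-up thresholds for one-claim subjects could serve as the window, but the choice should be stated as a linkage choice.
2. Do not collapse where dose-specific codes identify two distinct doses. The listed pairs 0001A/0002A and 0011A/0012A appear to serve this purpose; Table 2 does not label them, so their meaning should be written in.
3. Take the second dose from the next distinct date, and state that subjects with three or more claims are handled this way.
4. Report the number of claims collapsed, and repeat the Aim 2 analysis without collapsing as a sensitivity analysis.

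The cost is a few lines in Table 2 and one extra run. The downside is that a few genuine short-interval second doses without dose-specific codes would be treated as duplicates; they can be listed. This is a rule for pairing records and says nothing about dosing.
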